## Study Duration

The expected duration of the study is 1 year, assuming a weekly enrollment of 3 patients. For each enrolled subject, their participation in the study concludes at the 24-hour post-awakening follow-up after intravenous general anesthesia.

## Concomitant medications and medical treatments

The ACTIVA control system is used during intravenous general anesthesia for elective surgical procedures. During the operation of the ACTIVA software, the surgical procedure is ongoing. However, the ACTIVA control system does not interfere with the surgical procedure in any way.

For clinical needs, medications that interact with propofol and remifentanil may be administered. However, with the ACTIVA control system, there are no additional risks compared to the normal clinical practice of TIVA regarding these interactions. However, these medications could alter the interpretation of the outcome measures used to evaluate the secondary objective of the study. For this reason, the experimenter records the use of such medications in the notes section of the GUI so that this event is documented in the report file and can be considered during the analysis of the results.

## Follow-up

Each enrolled patient was reassessed 6 hours and 24 hours after awakening from anesthesia during the postoperative anesthesia visits.

## Clinical Investigation Plan

Automatic Control of Total Intravenous Anesthesia: Closed-loop Delivery of Propofol and Remifentanil Using Bispectral Index as Feedback Variable.

Acronym: ACTIVA 2. Id code: NP-2861. NCT number: NCT04432974.

## Statistical analysis

The statistical analysis consists in the descriptive statistics of the collected data.

Synthetic statistical data are calculated for all study variables.

For quantitative data mean and standard deviation, or median and interquartile range are calculated according to data distribution. Data normality is checked by using the Shapiro-Wilk test.

Categorical variables are synthesized by using patient count and percentage of patients belonging to each category.

## Systematic errors prevention methods

### Interaction between the ACTIVA software and the experimenter.

The user interface has been developed to make it easy for the experimenter to initiate the infusion system. Specifically, once the necessary connections between the monitor, PC, and infusion pumps have been set up, the experimenter can start the ACTIVA software and quickly check for any issues with the system. The software only starts when the experimenter has entered all the required data for startup, and the connections between the devices are correct and functioning. If the experimenter has not entered all the required data or if the devices are not functioning correctly or have not been turned on, the ACTIVA software cannot begin the infusion phase. This ensures both adequate safety and prevents incorrect or incomplete operation.

### Selection bias during patient recruitment.

The clinical trial recruits patients to undergo intravenous general anesthesia for elective surgery. The experimentation takes place in a single operating room of the experimenter's center where plastic surgery procedures are performed, ensuring a constant surgical and environmental setting. Patient selection, excluding those under 18 years of age, is done regardless of age, gender, weight, height, anesthesiologic risk, or type of surgical procedure. This reduces systematic errors associated with specific patient selection.

### Selection bias at the time of analysis.

The clinical trial requires that closed-loop anesthesia be practiced from the initiation of the ACTIVA software until the end of the surgical procedure. However, it may happen that:

- The primary experimenter decides to interrupt the software; in this case, it must be recorded in the report file.
- The software or its components (monitors, infusion pumps) may cease to function correctly; in this case, the system is halted and switches to manual mode or requires the experimenter's intervention. The experimenter must record the event in the report file. If the above occurs, it is the responsibility of the experimenter to assess the possibility of including in the data analysis what has been collected up to the moment of system interruption.

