### Clinical study description

The clinical study ACTIVA 2 is a pragmatic, interventional, nonrandomized, single-arm, single-center.

The investigation is for research purposes (for publication in scientific journals), non-commercial, and for clinical development of the ACTIVA control software.

The primary outcome measure is the depth of hypnosis adequacy. It is assessed by means of the percentage of the anesthesia maintenance duration in which the BIS is kept inside the recommended range from 40 to 60. The percentage of the anesthesia maintenance duration in which the BIS is kept below 40 is also specified. Maintenance duration is the period of time that goes from the end of anesthesia induction to the point at which the automatic control is turned off at the conclusion of surgery. The end of anesthesia induction is defined as the time instant when the BIS drops below 40 for the first time and remains there for the subsequent 30 seconds.

The secondary outcomes measures are:

- Number and types of dysfunctions of the ACTIVA automatic infusion system.
- Level of satisfaction of the experimenter. It is expressed on a scale from 0 to 10 regarding the ease of use of the ACTIVA software and its infusion system, the induction phase of anesthesia and the maintenance phase of anesthesia.
- Effect of drugs delivery on heart rate. It is assessed by means of the percentage of the anesthesia maintenance duration in which the heart rate (HR) is kept inside the range from 50 to 100 beats per minute. The percentage of the anesthesia maintenance duration in which the HR is kept below 50 is also specified.
- Effect of drugs delivery on mean blood pressure. It is assessed by means of the percentage of the anesthesia maintenance duration in which the non-invasively measured mean blood pressure (MBP) is kept inside the range from 65 to 110 mmHg. The percentage of the anesthesia maintenance duration in which the MBP is kept below 65 is also specified.
- Postoperative heart rate stability. It is assessed by measuring the HR in bpm.
- Postoperative Mean Blood Pressure Stability. It is assessed by non-invasive measuring of the mean blood pressure in mmHg.

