## Subject Enrollment Count

All subjects enrolled in the clinical investigation (including patients withdrawn from the study before its initiation who have provided informed consent and patients lost to follow-up) must be counted and documented. If a subject withdraws from the study, the reasons should be documented and recorded. These patients will not be included in the sample size calculation for the study or in the primary or secondary objectives.

Patients who are withdrawn from the study before the initiation of the ACTIVA software due to device safety, reliability, or feasibility issues are considered enrolled in the study and will be followed throughout the study's duration.

Patients who discontinue the study during the operation of the ACTIVA software are considered fully enrolled, and all available data will be analyzed.

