#### **Instrument-phenomenon interaction.**

The system relies on feedback control in which infusion rates are regulated by software after receiving BIS data to maintain the desired level of hypnosis. It is likely that the control system is better able to maintain the desired BIS level compared to manual control with or without TCI. If the primary experimenter observes an inability to maintain the BIS within the desired range despite apparent correct software operation, they may choose to suspend the software and switch to manual mode. This should be noted in the designated notes section and recorded in the report file.

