#### **Clinical Investigation Plan**

Automatic Control of Total Intravenous Anesthesia: Closed-loop Delivery of Propofol and Remifentanil Using Bispectral Index as Feedback Variable.

Acronym: ACTIVA 2. Id code: NP-2861. NCT number: NCT04432974.

will be interrupted, and the manufacturer will assess for a prompt solution. Only after producing a reliable version of the ACTIVA software can the clinical investigation resume. It is possible that the monitor or one or both of the pumps may experience malfunctions during the clinical investigation. These malfunctions are not attributed to the ACTIVA software but will be recorded in the report file and evaluated during the results analysis. Repairing or replacing the faulty device resolves the issue.

It is possible that the primary experimenter may decide to discontinue the control system to switch to manual control or another anesthesiological technique, noting the choice, which will be recorded in the report file. Switching to manual control or another anesthesiological technique is possible at any time if the experimenter deems it appropriate, even in the absence of system malfunctions.

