## Deviations from the clinical evaluation plan

Except in cases of necessity, the principal investigator is not authorized to deviate from the clinical protocol. Deviations from the clinical evaluation plan that are decided upon by the investigator to protect the rights, safety, and health of the patient will be documented and communicated to the manufacturer and the sponsor as soon as possible.

The sponsor will define the level of deviations as major or minor and will present them to the relevant Ethics Committee for evaluation accordingly. Major deviations are defined as changes in the conduct of the clinical investigation compared to the current protocol that could compromise the subject's rights, safety, health, completeness, accuracy, or scientific integrity of the data.

Deviations should be reported to the principal investigator and recorded in the patient's chart. Cases where a regularly enrolled patient does not complete the study due to ACTIVA software issues or at the investigator's discretion are not considered deviations; the patient will not be considered for secondary outcome measures but will be evaluated for the primary outcome measure.

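### Whether data from an interrupted session are analysed is left to the experimenter without criteria, and the SAP has no analysis set or rule for interrupted sessions

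*Protocol*

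**What the plan says.** Three protocol sections bear on a session that does not run to the end under automatic control.

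- *Selection bias at the time of analysis* lists two events: the experimenter decides to interrupt the software, or the software, monitor or pumps stop working correctly. It then says that "it is the responsibility of the experimenter to assess the possibility of including in the data analysis what has been collected" before the interruption.
- *Deviations from the clinical evaluation plan* covers an enrolled patient who "does not complete the study due to ACTIVA software issues or at the investigator's discretion": "the patient will not be considered for secondary outcome measures but will be evaluated for the primary outcome measure".
- *Subject Enrollment Count* says: "Patients who discontinue the study during the operation of the ACTIVA software are considered fully enrolled, and all available data will be analyzed".

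Related text:

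- *Study Duration* says of each subject that "their participation in the study concludes at the 24-hour post-awakening follow-up".
- *Instrument-phenomenon interaction* allows a switch to manual control when the experimenter "observes an inability to maintain the BIS within the desired range despite apparent correct software operation".
- *Factors that may compromise the outcome and interpretation of the results* says of monitor and pump faults: "These malfunctions are not attributed to the ACTIVA software but will be recorded in the report file and evaluated during the results analysis".
- The first secondary outcome in *Clinical study description* is "Number and types of dysfunctions of the ACTIVA automatic infusion system".

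In the SAP, *Population to be analyzed* repeats the eligibility criteria and study procedures. *Analyses* lists variables and descriptive statistics. Neither names an analysis set or mentions interrupted sessions.

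**The concern.** The study is single-arm and unblinded, and its primary result is a summary of how well BIS was held between 40 and 60. A person who has seen the trace may judge whether a partial recording enters that summary, with no stated criterion, timing or independent check. Inclusion can then depend on the result. If the wording means only a check that the recording is usable, the plan does not say what makes it usable.

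A second matter touches the reliability objective. If patients whose session the software failed to finish are left out of all secondary outcomes, they are left out of the count of dysfunctions, where they matter most.

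**Working it through.** **Step 1: do the sections conflict?** This turns on whether a software stop means that the patient has not completed, or has discontinued, the study.

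- If it does, there are three answers. *Selection bias at the time of analysis* makes inclusion optional. *Deviations* makes the primary outcome mandatory and removes the patient from secondary outcomes. *Subject Enrollment Count* has all available data analysed. The last two also disagree with each other on secondary outcomes. The wording of *Deviations*, which speaks of non-completion caused by software issues, favours this reading.
- If it does not, because participation runs to the 24-hour visit (*Study Duration*), *Deviations* and *Subject Enrollment Count* may not reach a patient whose software stopped but who attended that visit. The contradiction goes, and the undefined discretion is the only specific rule left.

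Monitor and pump faults are not attributed to the software, so the software clause of *Deviations* may not cover them on either reading.

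**Step 2: which stops fall under the discretion?** The sentence refers back to what precedes it without saying whether that is both listed events or only the malfunction. If both, it includes stops made because BIS could not be held in range. If only malfunctions, it does not.

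**Step 3: scale from the plan's own figure.** Inputs from *Number of patients enrolled*: expected proportion 90%, 95% confidence, n = 139.

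- 1.96² × 0.9 × 0.1 / 0.05² = 138.3, rounded up to 139. The stated size is reproduced with a half-width of 5 points.
- Half-width at n = 139: 1.96 × √(0.09/139) = 5.0 points.

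**Step 4: mean percentage in range.** Assumed: k patients omitted who average d points lower.

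- d measured from the retained mean: shift = k/139 × d. For k = 10: 10/139 × 20 = 1.4 and 10/139 × 40 = 2.9 points.
- d measured from the full-cohort mean: shift = k/(139 − k) × d. For k = 10: 10/129 × 20 = 1.6 and 10/129 × 40 = 3.1 points.
- For k = 3, both give 0.4 to 0.9 points.
- If 10 omitted patients average 20 points higher, the mean falls by 1.4 or 1.6 points.

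For comparison, the 95% half-width of a mean at n = 139 is 1.96 × SD/√139, or 1.7 to 3.3 points for an assumed SD of 10 to 20.

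**Step 5: proportion above 43%.** This proportion is named only in the sample-size text. Assumed: 10 omitted patients, none above 43%.

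- 90% holds among the retained 129: full-cohort value 0.9 × 129/139 = 83.5%, a rise of 6.5 points.
- 90% holds among all 139: 0.9 × 139/129 = 97.0%, a rise of 7.0 points.

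Both exceed the 5.0-point half-width.

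**Step 6: dysfunction count.** Extreme case: 10 of 139 patients have a dysfunction, each a session-ending software failure.

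- All patients counted: 10/139 = 7.2%, exact two-sided 95% interval 3.5 to 12.8%.
- *Deviations* taken literally: 0/129, upper limit 1 − 0.025^(1/129) = 2.8%.

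**The case against.** **The sections can be read together.** The experimenter is asked to assess a possibility, so the text may mean only that the patient is evaluated for the primary outcome and someone checks whether the partial recording is usable. A reader might infer a flat contradiction between the sections. The documents do not support that, because it depends on what completing the study means. What stands is the lack of criteria, which remains on every reading.

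**The bias may not be upward.** A reader might infer that the discretion inflates the result. That needs stops for poor BIS control to fall under it, and the back-reference does not settle this. If only malfunctions are covered, omitted sessions could be better or worse than average.

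**The cut-off can be inferred.** The maintenance window in *Clinical study description* and SAP *Outcomes* ends when automatic control is turned off at the conclusion of surgery. Together with the reference to data up to the interruption, a natural end point follows. This stands in part: the end point is inferable but not stated, and a session stopped before induction ends has no maintenance time at all.

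**There are safeguards.** Interruptions must be recorded, and a report file is always generated. *Clinical investigation monitoring plan* has the principal investigator and advisory board verify that data are reported correctly and review the software monthly against the primary outcome. *Data management* in both documents says in general terms that all described data are included. These weigh against silent omission and make it traceable, but none sets in advance who is analysed.

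**The dysfunction example is extreme.** It needs every dysfunction to be a session-ending software failure. Monitor and pump faults may not be removed, and the protocol says they are evaluated in the results analysis. The example shows the direction of the literal rule, not a forecast.

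**Conclusion.** The concern holds and should be fixed. The firm part is that inclusion of interrupted sessions is left to the experimenter without criteria, and that neither the SAP nor the monitoring arrangements supply an analysis set or a rule. The conflict with *Deviations* and *Subject Enrollment Count*, and between those two on secondary outcomes, is conditional on a software stop counting as non-completion or discontinuation. Upward bias is conditional on stops for poor BIS control falling under the discretion.

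The size depends on an interruption rate that the documents do not give. With three patients omitted, the effect on the mean is small. With ten, it approaches the mean's own half-width under the assumed SDs, and for the proportion above 43% it exceeds the half-width implied by 139 patients if none of the ten is above 43%. The literal removal of software-failed patients from the dysfunction count is a separate defect, and its effect is to make the device look more reliable.

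**What to change.** Delete the discretion in *Selection bias at the time of analysis*, reconcile that section with *Subject Enrollment Count* and *Deviations*, and state in both protocol and SAP:

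- (a) Every patient in whom automatic control was started is in the primary analysis set.
- (b) All closed-loop maintenance data up to the final switch to manual are analysed. *Measurement bias during data collection* provides for a switch to manual when a BIS problem persists, and some faults need only intervention; the documents do not say whether automatic control can resume. If it does, the later closed-loop time is kept, and the handling of the manual interval is stated in advance.
- (c) Patients stopped before the end of induction are counted and reported separately.
- (d) All started patients are in the dysfunction count. For each other secondary outcome, the SAP states whether interrupted patients count.

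Report the number, timing and reasons of interruptions, and give the planned mean or median with and without interrupted sessions, which shows any effect in either direction.

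The cost is a few sentences and one table. No new data are needed, since report files are always generated and dysfunctions are already collected. The result may be slightly less favourable. When to switch to manual control is not changed.

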### Measurement bias during data collection.

It is possible that during the operation of the ACTIVA software, there is a failure to read the BIS or a disturbance causing artifacts. The absence of a BIS signal or its distortion is not uncommon during normal clinical practice and is indirectly reported by the SQI and on the patient monitor. Such problems are usually caused by poor adherence of the BIS Quattro sensor to the skin. The experimenter can resolve the issue without consequences for the

### Clinical Investigation Plan

Automatic Control of Total Intravenous Anesthesia: Closed-loop Delivery of Propofol and Remifentanil Using Bispectral Index as Feedback Variable.

Acronym: ACTIVA 2. Id code: NP-2861. NCT number: NCT04432974.

infusion system. During the software development phase, these events have been anticipated, and appropriate filters and event checks have been incorporated, allowing for short-term toleration of BIS signal deficiencies (both qualitative - disturbances, and quantitative - signal absences). If the problem persists beyond 30 seconds or the experimenter deems it necessary, the system switches to manual mode. It should be emphasized that the BIS Monitor is an approved and certified instrument and undergoes regular maintenance by the clinical engineering service of the experimenter's center.

It is possible that during the operation of the ACTIVA software, there may be an issue with the infusion of one or both drugs due to malfunction or lack of control of the pumps (either one or both). The pumps are periodically checked and tested by the clinical engineering service of the experimenter's center, minimizing risks. In case of lack of control by the ACTIVA software, the pump emits an audible signal, and the user interface highlights the lack of connection on the corresponding pump with a red light. This allows the primary experimenter to rectify the problem or decide to halt the infusion system. During simulations, no issues with the infusion pumps were identified, and the infusion rates corresponded to what was commanded by the ACTIVA software and indicated on the GUI. This was made possible by developing a control system that respects the maximum infusion rates that the pump is capable of, in accordance with its mechanical components.

#### **Instrument-phenomenon interaction.**

The system relies on feedback control in which infusion rates are regulated by software after receiving BIS data to maintain the desired level of hypnosis. It is likely that the control system is better able to maintain the desired BIS level compared to manual control with or without TCI. If the primary experimenter observes an inability to maintain the BIS within the desired range despite apparent correct software operation, they may choose to suspend the software and switch to manual mode. This should be noted in the designated notes section and recorded in the report file.

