More recent studies have shown encouraging results when closed-loop systems involve both propofol and remifentanil.

Orliaguet, comparing two groups of pediatric patients undergoing scheduled surgeries lasting at least one hour, demonstrated that administering Propofol and Remifentanil through a closed-loop system controlled by BIS values is correlated with a higher percentage of time in which BIS remains within the predefined range (40-60). This results in a lower percentage of time when BIS falls below 40 compared to manual control (Orliaguet GA, 2015). Similar results were obtained by Liu in a multicenter randomized controlled study (Liu Y, 2015).

In a pilot study conducted on patients undergoing aortocoronary bypass surgery, in which a system for controlling all three components of anesthesia was used, it was possible to effectively complete the anesthesia procedure without any intervention by the anesthesiologist in 80% of cases (Zaouter C, 2016). The McSleepy system was also employed in a randomized controlled trial involving 186 patients undergoing surgeries lasting at least one hour. The results demonstrate that both hypnosis and analgesia are better controlled by the automatic system compared to the manual control group. Additionally, the

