## Number of patients enrolled

The sample size was determined based on the primary outcome measure concerning the depth of hypnosis adequacy provided by the ACTIVA control software. Specifically, it was calculated with the aim to assess the proportion of patients for whom the percentage of the anesthesia maintenance duration in which the BIS is kept inside the recommended range from 40 to 60 is greater than 43%. This latter value is the average percentage that was observed in a previous data acquisition campaign concerning manually controlled TIVA, which was performed in the same clinical setting considered for the present clinical trial (Study acronym: ACTIVA 1, Id code: NP-1843).

The proportion was estimated to be 90% of patients with a 95% confidence interval and a margin of error of 10%. The resulting sample size is 139 patients. This number of enrolled subjects also ensures that the ACTIVA control software is adequately tested for safety, reliability, feasibility, and applicability. Secondary outcome measures were not considered in the sample size calculation.

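### The plan gives no score for a session switched to manual because BIS could not be held; on the most natural reading such a session can still exceed 43%

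*Protocol*

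**What the plan says.** **Switching.** Under Instrument-phenomenon interaction, the Protocol provides: "If the primary experimenter observes an inability to maintain the BIS within the desired range despite apparent correct software operation, they may choose to suspend". Control then passes to manual mode. The event must be noted in the report file. No consequence for the score is stated.

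**Primary outcome.** Clinical study description (Protocol) and Outcomes (SAP) use the "percentage of the anesthesia maintenance duration in which the BIS is kept inside the recommended range from 40 to 60". Maintenance runs from "the end of anesthesia induction to the point at which the automatic control is turned off at the conclusion of surgery".

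**Interrupted sessions.** Three Protocol sections bear on them:
- Subject Enrollment Count: patients who discontinue while the software is running are fully enrolled, and whatever data exist are analysed.
- Selection bias at the time of analysis: the experimenter judges whether to include "what has been collected up to the moment of system interruption".
- Deviations from the clinical evaluation plan: when a patient does not complete because of software issues or at the investigator's discretion, "the patient will not be considered for secondary outcome measures but will be evaluated for the primary outcome measure".

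**Sizing.** The 139 patients were chosen to estimate the share of patients who meet this condition: "the percentage of the anesthesia maintenance duration in which the BIS is kept inside the recommended range from 40 to 60 is greater than 43" per cent (Protocol, Number of patients enrolled; SAP, Sample size calculation).

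**SAP.** It has no rule for a switch during surgery. Population to be analyzed repeats the recruitment text, and Analyses plans descriptive statistics only.

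**The concern.** The reason for this kind of switch is failure on the primary variable itself. If the switch also closes the measurement window, then the sooner a failing session is stopped, the less out-of-range time is counted. A session in which automatic control was abandoned could then be summarised as above the 43% benchmark. That would affect both the per-patient percentage and the proportion on which the trial was sized.

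The failure may not show elsewhere either. The Deviations section removes these patients from the secondary outcomes, which include system dysfunctions and experimenter satisfaction. A switch made while the software appears to work correctly also need not be logged as a dysfunction.

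**Working it through.** **1. The plan's own figure.** Inputs from the sample-size text: p = 0.90, 95% confidence, margin 10%. With n = z²p(1−p)/w²:
- w = 0.05: 1.96² × 0.09 / 0.05² = 138.3, rounded up to 139. This reproduces the plan.
- w = 0.10: 34.6, rounded up to 35. This does not.

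The 10% is therefore the total width of the interval. The half-width at 139 patients is 1.96 × √(0.09/139) = 0.050, or 5 points. That is the yardstick below.

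**2. What score does a switched session get?** The window ends at one event, "to the point at which the automatic control is turned off at the conclusion of surgery". A switch during surgery separates the two parts of that event, which leaves three readings:
- *Window ends when automatic control ends.* This is the most natural reading, because the only description of what an interrupted session contributes is data up to the interruption. Score = in-range time before the switch / time before the switch.
- *Window runs to the end of surgery, manual phase included.* Time held in range by the anesthesiologist is credited to the device.
- *Data left out at the experimenter's discretion.* The session disappears from the outcome, although the Deviations section says it is evaluated.

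Under none of the three does abandonment for failed control itself count against the controller.

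**3. One session (illustrative minutes).** Maintenance is 90 min. BIS is in range for 20 of the first 30 min and then out of range for 10, and the switch comes at minute 40.
- Up-to-switch: 20/40 = 50%, above 43%.
- Time kept in range by the system, over the whole maintenance: 20/90 = 22%.
- Manual phase counted, 25 of the remaining 50 min in range: 45/90 = 50%. All 50 in range: 70/90 = 78%.

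**4. When the classification flips.** Let r be the in-range share before the switch and f the fraction of maintenance completed at the switch. The up-to-switch score is r. With post-switch time not credited to the system it is r × f. A session with r > 0.43 passes on the former and fails on the latter when f ≤ 0.43/r:

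| r | switch before this fraction of maintenance |
|---|---|
| 0.5 | 86% |
| 0.7 | 61% |
| 0.8 | 54% |

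**5. Effect on the proportion.** Each reclassified patient moves it by 1/139 = 0.72 points. The documents give no switch rate, so 5% and 10% are assumptions. Start from 125/139 = 89.9% and suppose that all switched sessions exceed 43% on pre-switch time:

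| Switched | Scored up to switch | Left out | Counted as not above 43% (exact 95% CI) |
|---|---|---|---|
| 7 (5%) | 89.9% | 118/132 = 89.4% | 118/139 = 84.9% (77.8 to 90.4) |
| 14 (10%) | 89.9% | 111/125 = 88.8% | 111/139 = 79.9% (72.2 to 86.2) |

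The shift is 7/139 = 5.0 points or 14/139 = 10.1 points. Leaving the sessions out hides nearly all of it.

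**The case against.** **Pre-switch scoring is not a stated rule.** This stands. The window definition mentions the end of surgery, and the section on interruptions only asks the experimenter to consider including the earlier data. A reader might infer that the plan prescribes truncation at the switch. It does not; the defect is an undefined score.

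**Truncation need not flatter the device.** This also stands. Out-of-range time before the switch still lowers the score, and control might have recovered. With 12 of 40 min in range (30%), had automatic control continued and held 40 of the next 50, the result would have been 52/90 = 58%. The direction is fixed only against a denominator in which post-switch time is not credited to the system. For the same reason, the 22% above measures what the system delivered over the case. It does not predict what automatic control would have achieved had it continued.

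**The size is uncertain.** This stands. A reader might take a 20% switch rate from the cited pilot study, where "it was possible to effectively complete the anesthesia procedure without any intervention by the anesthesiologist in 80% of cases". That figure concerns any intervention, with a different system controlling three components of anesthesia, in coronary bypass surgery. It does not support a rate of switching for failed BIS control in a plastic-surgery room. Nor do the documents say what share of switched sessions would exceed 43%.

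**The primary outcome has no success criterion.** This is correct: it is a continuous percentage, summarised descriptively. The 43% cut-off appears only in the sample-size text, but that text says the proportion above it is what the trial was sized to estimate.

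**Performance while control is running is a legitimate target.** It is, and the up-to-switch value should be kept. On its own, though, it cannot show that control had to be abandoned.

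**Conclusion.** The concern holds as a gap with a material consequence. The plan keeps patients switched for failed BIS control in the primary outcome, gives them no score, and contains sections that do not fit together for a switch during surgery. On the most natural reading an abandoned session can exceed 43%, and the alternative readings do not count the failure against the controller either.

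The effect is 0.72 points per affected patient. It is about 5 to 10 points on the proportion if 5-10% are switched and all of them pass on pre-switch time, against a half-width of 5 points. Both conditions are assumptions; if fewer switched sessions pass, the shift shrinks in proportion. A reader might conclude that the primary result is certain to be inflated. The documents do not support that, because they fix neither the scoring rule nor the frequency of such switches.

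**What to change.** Reconcile the window definition (Protocol, Clinical study description; SAP, Outcomes) with Subject Enrollment Count, Selection bias at the time of analysis, and Deviations from the clinical evaluation plan, so that a switch during surgery has one stated treatment and inclusion is not left to the experimenter. Then pre-specify in the SAP, beside the up-to-switch percentage:

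- (a) the proportion above 43%, with every patient whose automatic control ended early because BIS could not be held counted as not above 43%;
- (b) the percentage with the denominator run to the end of surgery and post-switch time not credited to the system;
- (c) the number of switches by reason. Monitor, pump and software malfunctions and other discretionary switches should be tabulated separately and counted as failures only in a sensitivity analysis. The Protocol itself does not attribute monitor and pump faults to the software.

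Require the reason for each switch to be noted. The Protocol asks for the event to be recorded but does not expressly ask for the reason, and it accepts that entries may be forgotten.

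**Cost.** A few SAP sentences, a little more analysis, and possibly a slightly less favourable figure. Analysis (a) needs only the switch and its reason; (b) also needs the end-of-surgery time for switched cases. The clinical decision on when to switch is untouched.
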